## **9.0 Safety Analyses**

### **9.1 General Considerations**

Safety analyses will include adverse events, laboratory, and vital sign measurements. Safety data will be summarized by treatment group using the safety populations as defined in Section 4.0. For the Week 16 analysis, safety analyses will be conducted among the Safety Population in Period A and among the ALL\_RZB Population.

For the safety analysis, subjects are assigned to a treatment group based on the first dose actually received in each treatment period, regardless of the treatment randomized.

Missing safety data will not be imputed.

### **9.2 Adverse Events**

Adverse events (AEs) will be summarized and presented using primary MedDRA System Organ Classes (SOCs) and preferred terms (PTs) according to the version of the MedDRA coding dictionary used for the study at the time of database lock. The actual version of the MedDRA coding dictionary used will be noted in the AE tables and in the clinical study report. Specific adverse events will be counted once for each subject for calculating percentages, unless stated otherwise. In addition, if the same adverse event occurs multiple times within a subject, the highest severity and level of relationship to investigational product will be reported.

## 9.2.1 Treatment-Emergent Adverse Events

TEAEs are defined as follows for the safety population in each treatment period and the ALL\_RZB population.

### **TEAEs for Period A:**

For subjects who do not enter Period B, TEAEs are defined as any event with an onset or worsening date on or after the first dose of study drug and no more than 140 days after the last dose of study drug.

For subjects who enter Period B, TEAEs are defined as any event with an onset or worsening date on or after the first dose of study drug in Period A and before the first dose of study drug in Period B.

### **TEAEs for Period B:**

TEAEs are defined as any event with an onset or worsening date on or after the first dose of study drug in Period B and no more than 140 days after the last dose of study drug in the study.

### **TEAEs for All RZB:**

TEAEs are defined as any event with an onset or worsening date on or after the first dose of risankizumab and no more than 140 days after the last dose of risankizumab in the study.

Events where the onset date is the same as the study drug start date are assumed to be treatment-emergent. All treatment-emergent AEs will be summarized overall, as well as by primary MedDRA SOC and Preferred Term. The SOCs will be presented in alphabetical order, and the PTs will be presented in alphabetical order within each SOC.

The number and percentage of subjects experiencing treatment-emergent AEs will be summarized.

Pre-treatment AEs will be summarized separately.

### **9.2.2 Adverse Event Overview**

An overview of AEs will be presented consisting of the number and percentage of subjects experiencing at least one event for each of the following AE categories:

- Any TEAE
- Any TEAE related to study drug according to the investigator
- Any severe TEAE
- Any serious TEAE
- Any TEAE leading to discontinuation of study drug
- Any TEAE leading to death
- Treatment-emergent Areas of Safety Interest (ASIs) as specified in [Appendix B](#)
- All deaths

### **9.2.3 Treatment-Emergent Adverse Events by SOC and/or PT**

The above TEAE categories will be summarized by SOC and PT; by maximum relationship to study drug as assessed by the investigator (e.g., reasonable possibility or no reasonable possibility) and SOC and PT; by maximum severity and SOC and PT; and by subject number and SOC and PT. Specific adverse events will be counted once for each subject for calculating percentages, unless stated otherwise. In addition, if the same adverse event occurs multiple times within a subject, the highest severity and level of relationship to investigational product will be reported.

In addition, treatment-emergent adverse events will be summarized by PT and sorted by decreasing frequency in the combined risankizumab group.

#### **9.2.4 Treatment-Emergent Adverse Events per Patient-Years of Exposure**

Exposure-adjusted AEs per 100 patient-years will be provided, where AEs per 100 patient-years of exposure are defined as the number of AEs divided by the total exposure in 100 patient-years.

Note that one event per preferred term per day per subject will be counted in the calculation of the number of AEs (i.e., a preferred term will not be counted twice on the same day for the same subject). See the calculation method below.

$$100 \times \frac{\text{Number of TEAEs}}{\text{Total Patient Years}},$$

where total patient years is defined as the sum of the study drug exposure (defined as date of last dose – date of first dose + 140 days (5 half-lives)) of all subjects normalized by 365.25 and rounded to one decimal place.

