### 7.4 Statistical Analyses for Safety

---

All safety analyses will be performed on the Safety Population for both treatment periods, respectively, based on the treatment subjects actually receive. Safety will be assessed by AEs, laboratory tests, vital signs, and ECG variables. Missing safety data will not be imputed for safety analysis. Analysis details will be specified in the SAP. AEs will be coded using Medical Dictionary for Regulatory Activities (MedDRA). A treatment-emergent adverse event (TEAE) is defined as an AE with onset or worsening on or after the first dose of study drug and within 140 days (20 weeks) after the last dose of study treatment injection. The number and percentage of subjects experiencing TEAEs will be tabulated using MedDRA system organ class (SOC) and preferred term (PT), as well as by severity and by relationship to the study drug as assessed by the investigator. Summaries (i.e., number, percentages, and events per 100 patient-years) of TEAEs, SAEs, deaths, AEs leading to discontinuation, and ASI will be provided. Pre-treatment AEs will be summarized separately.

For laboratory test and vital signs variables, mean change from baseline and percentage of subjects with evaluations meeting criteria for pre-defined Potentially Clinically Significant (PCS) values will be summarized.

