### **Study Drug Exposure (in Days) in Each Period:**

In Period A, duration of treatment is defined as:

- For subjects who did not continue to Period B,
  - last injection date in Period A minus first injection date in Period A + 84 days.
- For subjects who continued to Period B, the minimum of
  - last injection date in Period B minus first injection date in Period A,
  - last injection date in Period A minus first injection date in Period A + 84 days.

In Period B, duration of treatment is defined as:

- last injection date in Period B minus first injection date in Period B + 84 days.

For ALL\_RZB population, duration of treatment is defined as

- date of last injection of risankizumab minus date of first injection of risankizumab + 84 days.

Duration of treatment will be summarized using the number of subjects treated, mean, standard deviation, median, minimum and maximum.

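### Person-time in SAP 9.2.4 runs past the end of the Period A event window, so Period A rates per 100 patient-years come out up to one third too low on the planned schedule

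*SAP*

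**What the plan says.** **Denominator.** SAP 9.2.4 divides the number of treatment-emergent events by total patient-years. Each subject's exposure is "date of last dose – date of first dose + 140 days (5 half-lives"). It names no period or population and sets no upper limit.

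**Numerator.** SAP 9.2.1 defines the event window separately for each analysis set.
- Period A, subjects who enter Period B: "on or after the first dose of study drug in Period A and before the first dose of study drug in Period B".
- Period A, subjects who do not enter Period B: from first dose to 140 days after the last dose.
- Period B: from the first Period B dose to 140 days after the last dose.
- All-risankizumab population (ALL_RZB): "on or after the first dose of risankizumab and no more than 140 days after the last dose of risankizumab in the study".

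**Where rates are needed.** Protocol 7.4 states: "All safety analyses will be performed on the Safety Population for both treatment periods, respectively". It also states: "Summaries (i.e., number, percentages, and events per 100 patient-years) of TEAEs, SAEs, deaths, AEs leading to discontinuation, and ASI will be provided". SAP 9.1 adds that at the Week 16 analysis "safety analyses will be conducted among the Safety Population in Period A and among the" ALL_RZB population.

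**A second exposure definition.** SAP 6.0 defines treatment duration with an 84-day tail. For Period A subjects who continue, it takes the smaller of two quantities, one of which is "last injection date in Period B minus first injection date in Period A". Section 9.2.4 does not use this definition.

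**The concern.** A rate per unit of person-time is meaningful only if every day in the denominator is a day on which an event could enter the numerator. For Period A subjects who continue, the numerator closes at the first Period B dose but the denominator runs to 140 days after the Week 4 dose, well into Period B. The extra days add exposure and no events.

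Placebo is given only in Period A, so every placebo rate per 100 patient-years is affected. Absolute Period A rates, and the rate differences between arms, shrink by the same factor. A reader who sets the placebo rate beside the final Period B or ALL_RZB rate would compare a deflated figure with a matched one. The SAP does not plan that comparison, but the tables invite it.

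The formula also credits days that have not been observed. This happens for ALL_RZB at the Week 16 data cut and for subjects who leave the study early.

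**Working it through.** The documents state no patient-years or event rates, so there is no printed figure to reproduce. The check is person-time arithmetic on the planned schedule.

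**Inputs**
- Doses on Days 0 and 28 (Period A) and Days 112, 196 and 280 (Period B): SAP 2.2.
- Tail of 140 days: SAP 9.2.4.
- Event windows: SAP 9.2.1.
- Arm sizes 31 (placebo), 62 and 62: SAP 2.4.
- Visit windows of ±3 days at Weeks 4 and 16: Protocol Appendix D.
- Share of subjects not entering Period B: not given. Assumed 5% to 20%.

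**Step 1. One subject.** Credited days D = last dose − first dose + 140. Event-window days W come from SAP 9.2.1. The reported rate equals the matched rate × W/D.

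| Case | D | W | W/D |
|---|---|---|---|
| Period A, two doses, continues | 28 + 140 = 168 | 112 | 0.667 |
| Period A, one dose, continues | 0 + 140 = 140 | 112 | 0.80 |
| Period A, two doses, does not continue | 168 | 168 | 1 |
| Period B, end of study | (280 − 112) + 140 = 308 | 308 | 1 |
| ALL_RZB, end of study | 280 + 140 = 420 | 420 | 1 |
| ALL_RZB, placebo switcher, end of study | 308 | 308 | 1 |

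With full follow-up, only Period A continuers fail to match. Within the ±3-day windows their factor runs from 109/171 = 0.637 (Week 4 on Day 31, Week 16 on Day 109) to 115/165 = 0.697 (Days 25 and 115).

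**Step 2. The arm.** With a share *q* not continuing, both doses given and non-continuers followed for their whole window, the factor is [(1 − q) × 112 + q × 168]/168.
- q = 0: 112/168 = 0.667 (33.3% low).
- q = 0.05: 114.8/168 = 0.683 (31.7% low).
- q = 0.20: 123.2/168 = 0.733 (26.7% low).

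**Step 3. Patient-years.**
- Placebo, 31 subjects: 31 × 168/365.25 = 14.3 credited. Matched: 9.5 (q = 0), 9.7 (q = 0.05), 10.5 (q = 0.20).
- Each dose arm, 62 subjects: 62 × 168/365.25 = 28.5 credited. Matched: 19.0, 19.5 and 20.9.

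**Step 4. Effect on comparisons.** If 5% of one arm and 20% of another do not continue, the rate ratio is biased by 0.733/0.683 = 1.07. For illustration, assume true rates of 300 and 400 per 100 patient-years. At q = 0 they are reported as 200 and 267: the ratio stays at 1.33, but the difference is 67 instead of 100. Beside a matched Period B or ALL_RZB rate, the placebo rate is distorted by 168/112 = 1.5-fold.

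**Step 5. ALL_RZB at the Week 16 cut.** Observed against credited days for single subjects:
- just dosed at Week 16, on risankizumab from the start: 112 against 112 + 140 = 252 (0.44);
- at Day 364: 364 against 420 (0.87);
- placebo switcher just dosed: 0 against 140.

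A subject who left early after both doses, with last contact on Day 60, gives 60/168 = 0.36.

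**Step 6. The other reading.** If *last dose* means last in the study, a Period A continuer is credited 420 days and the factor is 112/420 = 0.267.

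**Step 7. SAP 6.0.** After two or more Period B doses, the quantity using the last Period B injection (Day 196 or 280) exceeds 28 + 84 = 112, so the minimum never binds. The resulting overlap is small: Week 4 on Day 31 gives 31 + 84 = 115 against Week 16 on Day 109, or 6 days.

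**The case against.** **The formula is not labelled for Period A.** True: its use there is inferred. But Protocol 7.4 asks for safety by period and for rates per 100 patient-years, SAP 9.1 requires a Period A safety analysis, and no other rate denominator is given. A programmer following the SAP would apply it.

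**One third is not a hard limit.** Correct. It holds for period-specific doses, both given on schedule, with every subject continuing and full follow-up. An individual subject can reach 36.3% within the visit windows, early leavers can be worse, and the alternative reading of *last dose* is much worse.

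**The consequences are modest.** This stands. Rate ratios between arms within Period A are roughly preserved when continuation is similar. Subject percentages, serious event listings and efficacy are untouched, and no test uses these rates. The 56 days counted in both periods (168 − 112) distort no planned total, because the SAP does not add the two periods.

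**The Week 16 ALL_RZB effect has no group-level size.** Also true: it depends on enrolment timing, which the documents do not give. It disappears at study end for subjects followed for 140 days after their last dose.

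**Early leavers are few.** Plausible. Protocol 5.6 keeps subjects who stop study drug in scheduled visits, and Protocol 6.1 collects events for 140 days after discontinuation. Unobserved credit therefore arises mainly from withdrawn consent or loss to follow-up.

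None of this removes the mismatch for Period A continuers.

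**Conclusion.** The concern holds. Applied to Period A as written, SAP 9.2.4 counts person-time that the event definition in SAP 9.2.1 excludes. Absolute Period A rates per 100 patient-years, including every placebo rate, are about 27% to 33% too low if 0% to 20% of subjects do not continue. That range assumes both doses on schedule, period-specific first and last doses, and full follow-up of non-continuers. Rate differences shrink by the same proportion.

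That the window and the denominator disagree is clear from the text. The size is less certain, because it depends on continuation and on how *last dose* is read. At the Week 16 cut the ALL_RZB rate is also too low by an unknown amount, so the direction of any contrast with placebo at that cut is not fixed. This should be corrected before the rate tables are produced, but it does not threaten the trial's main conclusions.

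**What to change.** In SAP 9.2.4, define person-time separately for each population so that it ends with that population's event window:
- **Period A, subjects who enter Period B:** date of first Period B dose minus date of first Period A dose.
- **All others:** from the relevant first dose to the earliest of last dose + 140 days, last contact and data cut-off. The relevant first dose is the first Period A dose for Period A non-continuers, the first Period B dose for Period B, and the first risankizumab dose for ALL_RZB.

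As a minor correction in SAP 6.0, use the first rather than the last Period B injection in the Period A minimum, so that the cap works.

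The cost is a few SAP sentences and a changed derivation for the rate tables. No new data are needed and subjects are not affected.

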#### **9.2.5 SAEs (Including Deaths) and Adverse Events Leading to Study Drug Discontinuation**

SAEs (including deaths) and AEs leading to study drug discontinuation will be summarized by SOC and PT and in listing format.

#### **9.2.6 Area of Safety Interest**

Area of safety interest will be summarized by SOC and PT. The list of ASIs with their respective search strategies for each ASI category are provided in [Appendix B](#).

The final list will be based on the most updated final version of risankizumab Product Safety Statistical Analysis Plan, which is consistent to the most updated risankizumab Risk Management Plan.

Tabular listings of ASIs will be provided.

### 9.3 Analysis of Laboratory Data

Data collected from central and local laboratories, including additional laboratory testing due to an SAE, will be used in all analyses, except for Baseline where SAE-related laboratory assessments on or before the first dose of study drug, or values observed more than 140 days after the last dose of study drug will be excluded. The clinical laboratory tests defined in the protocol operations manual (e.g., hematology and clinical chemistry) will be summarized.

Each laboratory variable will be summarized for all time points (starting with Baseline) with the number of non-missing observations, mean and standard deviation, median, minimum and maximum. Mean change from baseline to each applicable post-baseline visit will be summarized for selected laboratory variables, with the number of observations, baseline mean, and visit mean. The change from baseline mean, standard error, and 95% confidence interval will be presented for the mean change from baseline within each treatment group and difference between treatment groups (risankizumab vs. placebo).

Changes in laboratory parameters will be tabulated using shift tables either by NCI CTC criteria or categorized as low, normal, or high based on the normal ranges of the laboratory used for each sample. A shift table from baseline either to the worst value (based on NCI CTC criteria) during treatment or to minimum and maximum value (based on normal range), will be created. A similar shift table will be provided to summarize shifts from baseline to the final post-baseline value.

Laboratory abnormalities meeting CTC criteria grade 3 and 4 will be summarized.

Laboratory abnormalities will be evaluated based on potentially clinically significant (PCS) criteria ([Appendix C](#)). For each laboratory PCS criterion, the number and percentage of subjects who have a laboratory value meeting the criteria will be summarized. Listings will be provided to summarize subject-level laboratory data for subjects meeting PCI criteria.

Additional summaries will be presented for liver function tests including ALT/SGPT, AST/SGOT, alkaline phosphatase, and total bilirubin, with laboratory values to be categorized as follows:

- $< 1.5 \times \text{ULN}$
- $\geq 1.5 \times \text{ULN} - < 3.0 \times \text{ULN}$
- $\geq 3.0 \times \text{ULN} - < 5.0 \times \text{ULN}$
- $\geq 5.0 \times \text{ULN} - < 10.0 \times \text{ULN}$
- $\geq 10.0 \times \text{ULN} - < 20.0 \times \text{ULN}$
- $\geq 20.0 \times \text{ULN}$

A listing of potentially clinically significant liver function laboratory values will include all subjects who met any of the following four criteria:

- $\text{ALT} \geq 3 \times \text{ULN}$ , or
- $\text{AST} \geq 3 \times \text{ULN}$ , or
- Alkaline phosphatase  $\geq 1.5 \times \text{ULN}$ , or
- Total bilirubin  $\geq 2 \times \text{ULN}$ .

A listing of possible Hy's Law cases, defined as those who meet all of the following conditions will be provided.

- $\text{ALT of } > 3 \times \text{ULN}$  or  $\text{AST of } > 3 \times \text{ULN}$ ,
- Associated with an increase in bilirubin  $\geq 2 \times \text{ULN}$ ,
- Alkaline phosphatase  $< 2 \times \text{ULN}$

## 9.4 Analysis of Vital Signs

Each vital sign variable will be summarized for all applicable time points (starting with Baseline) with the number of non-missing observations, mean and standard deviation, median, minimum and maximum. Mean change from baseline to each applicable post-baseline visit will be summarized for each vital sign variable, with the number of

observations, baseline mean, and visit mean. The change from baseline mean, standard error, and 95% confidence interval will be presented for the mean change from baseline within each treatment group and difference between treatment groups (risankizumab vs. placebo).

If applicable, summary statistics will also be provided for change from baseline height and weight at each scheduled visit for the adolescent group.

Vital sign variables will be evaluated based on potentially clinically significant (PCS) criteria ([Appendix C](#)). For each vital sign PCS criterion, the number and percentage of subjects who have a vital sign value meeting the criteria will be summarized. Listings will be provided to summarize subject-level vital sign data for subjects meeting PCS criteria.

## **9.5 Safety Subgroup Analyses**

There are no safety subgroup analyses planned for this study.

## **9.6 Other Safety Analyses**

There are no other safety analyses planned for this study.

## **10.0 Other Analyses**

There are no other analyses planned for this study.

## **11.0 Interim Analyses**

There are no interim analyses planned for this study.

## **11.1 Data Monitoring Committee**

An external data monitoring committee (DMC) composed of persons independent of AbbVie and with relevant expertise in their field will review unblinded safety data from

the ongoing study. The primary responsibility of the DMC will be to protect the safety of the subjects participating in this study.

A separate DMC charter describes the roles and responsibilities of the DMC members, frequency of data reviews, relevant data to be assessed, and general operations.

Since there are no efficacy analyses for early stopping, no alpha adjustment is needed.

## 12.0 Overall Type-I Error Control

[figure not shown]
The primary and key secondary efficacy endpoints for risankizumab 150 mg and 300 mg will be tested with a graphical multiple testing procedure to ensure strong control of family-wise type I error rate at two-sided significance level of 0.05. Specifically, the testing will utilize the endpoint sequence of primary endpoint followed by the ranked key secondary endpoints in the order as specified in [Table 1](#), and will begin with testing the primary endpoint using two-sided  $\frac{1}{2} \alpha$  of 0.025 for each comparison: risankizumab 150 mg vs. placebo and risankizumab 300 mg vs. placebo. Continued testing will follow a pre-specified  $\alpha$  transfer path ([Figure 2](#)) which includes downstream transfer along the endpoints sequence within each dose as well as cross-dose transfer. Adjusted p-values for the primary and key secondary endpoints will be provided based on the testing procedure.

The graph for the testing procedure is provided in [Figure 2](#). In the graph, the arrows specify the  $\alpha$  transfer path. Once the null hypothesis for an endpoint is rejected (i.e., deemed significant) at its assigned significance level, its significance level will be transferred to the subsequent endpoint(s) following the arrow(s). The numbers on the arrows denote the weights for transferring and (possibly) splitting significance levels. Specifically, the weight 1 denotes 100% transfer of significance level.

**Table 1. List of Primary and Key Secondary Endpoints**

Abbreviation	Endpoint
V1	Proportion of subjects achieving EASI 75 from Baseline at Week 16.
V2	Proportion of subjects achieving vIGA-AD of 0 or 1 with a reduction from Baseline of $\geq 2$ points at Week 16.
V3	Proportion of subjects achieving an improvement (reduction) of $\geq 4$ points in worst pruritus NRS from Baseline to Week 16.

